Hypothesis: We hypothesize that: relative to the control group, the PLASMA group will report greater improvement over time in (H1) quality of life (primary outcome), and (H2) asthma knowledge, attitudes, outcome expectations, self-efficacy, self-management skills, and asthma control, FEV1 (exploratory outcomes). (H3) The post-PLASMA scores on outcome measures will be higher than pre-program scores from both treatment groups.

- 2) To examine the mediating effects of the secondary outcomes (knowledge, attitudes, outcome expectations, self-efficacy, self-management skills, asthma control, and FEV1) on the primary outcome (quality of life) of the intervention.
- 3) To examine the moderating effects of personal factors (e.g., age, sex, family support) on primary and secondary outcomes of the intervention.
- 4) To evaluate the effects of PLASMA on primary and exploratory outcomes in peer leaders (16-20 years).

Hypothesis: We hypothesize that the peer leaders (n=42) will report significant improvement in quality of life (primary outcome) and secondary outcomes (knowledge, attitudes, outcome expectations, self-efficacy, self-management skills, asthma control and FEV1) over the course of 15 months.

- 5) To determine the economic impact of the intervention. This aim will be accomplished by (5a) measuring the direct healthcare costs and total costs of the PLASMA program, as compared with the control group; (5b) performing net cost analyses for each type of costs; and (5c) estimating cost-effectiveness ratios of the PLASMA group compared with the control.

Hypothesis: We hypothesize that the direct and overall costs per participant in the PLASMA group will be less than costs per participant in the control group, or cost neutral.

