4. METHODS AND STUDY PROCEDURES

4.1 Study Procedures and Assessments

Design: This study will use a two-group randomized controlled design implemented in three metropolitan cities: Buffalo, NY, Baltimore, MD, and Memphis, TN. The project coordinator and a research assistant in each city who are not involved in direct patient care of teens with asthma will be responsible for recruitment and consent process taking place in each site. Peer leaders will attend a three-day intense training session that will take place prior to camps, lead small-group instructional activities at a one-day camp (PLASMA group) and follow up their group members bimonthly for 15 months. Camp participants from each site (n=126) will be randomly assigned to the peer-led (PLASMA) group or the adult-led (control) group. Upon enrollment, participants will be stratified by gender and age (younger 12-14 years, older 15-17 years), and randomly assigned to either group within each of four blocks generated by the combination of gender and age strata. Each group will attend a separate day camp where an asthma self-management program will be implemented either by peer leaders (intervention) or healthcare professionals (control). After the camp, the intervention group will receive peer-leader contacts bimonthly for 14 months using phone calls or other communication technologies (e.g., emails, or short-message system (e.g., texting) of teens' choice. Adult instructors (healthcare professionals) will contact the control group bimonthly for 14 months using similar methods, but different contact topics.

Both groups (intervention and control – more details below) will provide data at enrollment (T1), 3 months later (T2), immediately following the camp (T3), and at 3-, 6-, 9-, 12-, and 15-months post-camp (T4-T8).

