		Cognitive factors				Self-management				Asthma control					
	PAQL	AA	AT	AS	AOE	ASM	AD-S	AD-O	FEF	ACT	AEC	FEV1	SD	PFS	
T1	✓	✓	✓	✓	✓	✓	✓	✓	✓	✓	✓	✓	✓	✓	✓
T2	✓	✓	✓	✓	✓	✓	✓	✓	✓	✓	✓	✓	✓	✓	
T3	✓	✓	✓	✓	✓	✓	✓	✓	✓	✓	✓	✓	✓	✓	
T4	✓	✓	✓	✓	✓	✓	✓	✓	✓	✓	✓	✓	✓	✓	
T5	✓	✓	✓	✓	✓	✓	✓	✓	✓	✓	✓	✓	✓	✓	
T6	✓	✓	✓	✓	✓	✓	✓	✓	✓	✓	✓	✓	✓	✓	
T7	✓	✓	✓	✓	✓	✓	✓	✓	✓	✓	✓	✓	✓	✓	
T8	✓	✓	✓	✓	✓	✓	✓	✓	✓	✓	✓	✓	✓	✓	

Measures for Cost-Effective Analysis:

Health care utilization and costs associated with asthma will be assessed by (1) Medicaid claims, and (2) medical record reviews. We expect that a majority of participants will be enrolled in Medicaid as 90-95% of inner-city children/adolescents were in previous studies conducted in Rochester, Baltimore and Memphis. The Medicaid claims (to be purchased from the Centers for Medicaid & Medicare Services [CMS]) will provide the best source of data for Medicaid-covered services including office visits, ED visits, inpatient care, and prescribed medications. The Medicaid administrative data contain detailed individual-level information on treatment and procedure codes (ICD-9-CM or CPT codes), service dates and expenditures. For adolescents whose services are not available from CMS data, detailed data on service use and prescribed medications related to asthma will be collected through medical records from PCPs; HIPAA authorization will be obtained from parents. In all sites, medical record review was approved by supporting practices for participants lacking CMS data. In both cases, data will be collected between 3 months before enrollment and 3 months after completion of the 15-month follow-up. At each time point, teens and parents will report the number of missed school days due to asthma and the number of hours missed from parents' gainful employment due to the teen's asthma in

the past 3 months.

Measures of Program Evaluation.

(a) Camp Program Evaluation (CPE:7 items) will be administered at the camp to assess the campers' perception about and overall satisfaction with the program.

(b) Overall Program Evaluation (OPE: 6 items) will be completed at 15-months follow-up to assess participants' overall perceptions about the study. Each item will be examined individually.

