Self-reported (standardized questionnaires) and physiological (PEFR and Spirometry) data collected longitudinally (21 months) will capture systematic and dynamic processes by which the program modifies adolescents' self-management behaviors and health outcomes. The long-term observation will also allow the investigators to examine the sustainability of the intervention. Inclusion of multiple cognitive factors (knowledge, attitude, self-efficacy, and outcome expectations) as mediators will allow us to demonstrate intricate interrelationships or mechanisms between the intervention and asthma outcomes including asthma control and quality of life in adolescents. This study will also systematically investigate the economic impact (e.g., healthcare utilization, prescription and indirect costs) of the intervention, which will offer invaluable data to policy makers who might consider adopting the intervention as a standard care for teens with asthma. Moreover, this multi-site study involving three cities representing the Northeastern, Eastern and Southern sections of the US will provide evidence of the generalizability of the intervention and its impacts, which could further accelerate the adoption and implementation of the program to address the serious health threats of asthma in inner-city adolescents and to contain economic costs to society.

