10. DATA ANALYSIS AND DATA MONITORING

10.1 Planned Statistical Analysis: Analyses will be performed using SAS, and R⁵⁶ will be used as analysis software to ensure the validity and reproducibility of the results. We will perform descriptive statistics on each outcome measure to look for abnormality and outliers. If a measure is not normally distributed, transformation will be applied. We will identify and investigate outliers for sources of errors, and conduct preliminary analyses on data distribution and bivariate correlations to determine the appropriate statistical model as well as the final interpretation of the results. We will investigate missing data with pattern analysis for data missing completely at random (MCAR), missing at random (MAR) or missing not at random (MNAR), and use statistical methods appropriate for each type such as maximum likelihood and multiple imputation to impute missing values so full analysis can be performed with sensitivity. We will compute Cronbach's alphas for psychometric measures, and assess construct validity using exploratory or confirmatory factor analysis when appropriate. The PLASMA and control groups will be compared on baseline data to determine any systematic differences; if any are found, analyses will include the variables as covariates in the model to adjust for the imbalances.

Aim 1: A multi-site hierarchical three-level linear mixed-effects model,^{26, 56, 57} where level 1 represents repeated measures, level 2 = subject, and level 3 = site, will be used to analyze treatment differences and treatment-by-time interaction described in the following notation by Hedeker and Gibbons.⁵⁷

Aim 2: The mediating effects will be examined mainly using the mediation methods of Baron & Kenny.⁵⁸ When found significant, a multiple mediation analysis⁵⁹ procedure will be used to further determine whether the effect of PLASMA on quality of life is mediated jointly by multiple exploratory outcomes.

Aim 3: Moderating effects will be examined by multiple linear models and generalized linear models described in Berridge and Crouchley⁵⁶ or Chen and Peace⁶⁰ along with the above multi-site hierarchical three-level linear mixed-effects models.

Aim 4: This aim will be tested by applying the multi-site hierarchical two-level linear mixed-effects models described in the analysis for Aim 1, with level 1 representing longitudinal measurements and level 2 sites.

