Aim 5: The costs of services received during visits to a physician's office, outpatient department, or ED will be estimated by taking the global relative value unit for each service CPT (Current Procedural Terminology) code multiplied by a standard conversion factor.⁶¹ Hospital charges will be converted to costs using department-specific cost-to-charge ratio.⁶² Medications and dosages prescribed will be captured; standard wholesale unit cost from the Pharmaceutical Red Book⁶³ will be used to estimate medication costs. To calculate lost productivity costs of a family with a sick teen, we will estimate total lost income related to each participant by multiplying total number of work hours missed by a parent's hourly wage. Program costs will be estimated from the actual time peer and adult leaders spent in carrying out the program multiplied by hourly earnings, costs of equipment/ supplies, and overhead costs; program time will not include staff time for research-related tasks. We will estimate the average program cost per participant by study group, and include this estimate as one component of direct healthcare costs. The

medical or general Consumer Price Index⁶⁴ will be used to inflation-adjust costs to current year prices.⁶⁴ For each teen at each time-point, we will calculate total direct costs, direct costs by major category (office visit, hospitalization), indirect lost-productivity costs, and total direct and indirect costs. For withdrawals from follow-up, we will impute missing utilization and cost data assuming a linear trend in use and cost given prior experiences, where we will estimate weighted least square regression on log-transformed cost and obtain smearing-retransformed predictions.⁶⁵ For PLASMA and control groups separately, we will calculate the cost difference between each time point and baseline for each teen, assuming (s)he received “standard care” before treatment. Cost differences for each group will be modeled against follow-up points and individual covariates to estimate the independent impacts of each program on costs relative to standard care.

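### Aim 5 compares costs between arms, but the plan analyses raw change from one baseline value; a joint two-arm model with pre-enrolment cost as a covariate estimates that contrast more precisely.

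*Combined protocol and SAP*

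**What the plan says.** Section 10.1, Aim 5, defines the cost outcome as a change score: "For PLASMA and control groups separately", "we will calculate the cost difference between each time point and baseline for each teen". The pre-treatment period is taken to represent standard care. The model is then described in one sentence: "Cost differences for each group will be modeled against follow-up points and individual covariates". Its purpose is to estimate each program's effect relative to standard care. The individual covariates are not listed, and the section describes no model containing both arms. The general rule earlier in Section 10.1 adds baseline variables only after an imbalance is seen: "if any are found, analyses will include the variables as covariates in the model".

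The hypothesis for Aim 5 in Section 1 is a between-arm statement: "direct and overall costs per participant in the PLASMA group will be less than costs per participant in the control group", or else costs are neutral.

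On data, Section 4.1 (Measures for Cost-Effective Analysis) says that "data will be collected between 3 months before enrollment and 3 months after completion of the 15-month follow-up". Missed school days and lost work hours are recalled over three months at every assessment.

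**The concern.** The quantity the hypothesis needs is the PLASMA-minus-control difference in cost. As written, the only route to it is to difference two separately estimated mean changes. Each teen's change carries the full variance of a single baseline quarter as well as that of the follow-up cost. Unless quarterly costs are strongly correlated, the subtraction adds more noise than it removes.

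At stake is the width of the interval for the cost difference. The trial is sized on quality of life (Section 2.1a), and no cost SD, correlation or target precision is stated for Aim 5. A needlessly wide interval makes a true saving and a true excess cost equally hard to detect, while the hypothesis allows either a saving or neutrality.

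**Working it through.** **The plan's own figure.** There is none for cost. The only sample size is for quality of life: 276/(1 − 0.27) = 378.08, which reproduces 378. The illustration below uses 276/2 = 138 completers per arm.

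**Which quarters exist.** T2 is three months after enrolment (Section 4.1) and is also called three months pre-camp (Section 4.4), so the camp is at month 6. This agrees with the 21-month span in Section 7.2 less 15 months post-camp. Cost data start three months before enrolment, giving nine pre-camp months, or three quarters. Section 4.4 lists baseline separately from the pre-camp visit, so I read baseline as T1 and its cost as that of the pre-enrolment quarter. T4 to T8 close five post-camp quarters.

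**Assumptions.** Equal quarterly variances and a common correlation r between quarters. The documents give neither, so r is varied. Variances are per teen, in units of one quarter's variance. V = (1 + 4r)/5 is the variance of a five-quarter mean.

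**Formulas.**
- One follow-up quarter: no adjustment 1; change score 2(1 − r); baseline quarter as covariate 1 − r².
- Mean of five quarters: no adjustment V; change score V + 1 − 2r; covariate V − r².

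| | r = 0.2 | r = 0.4 | r = 0.6 |
|---|---|---|---|
| One quarter, unadjusted | 1.00 | 1.00 | 1.00 |
| One quarter, change score | 1.60 | 1.20 | 0.80 |
| One quarter, covariate | 0.96 | 0.84 | 0.64 |
| Reduction against change score | 40% | 30% | 20% |
| Five-quarter mean, unadjusted | 0.36 | 0.52 | 0.68 |
| Five-quarter mean, change score | 0.96 | 0.72 | 0.48 |
| Five-quarter mean, covariate | 0.32 | 0.36 | 0.32 |
| Reduction against change score | 67% | 50% | 33% |

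**Direction.** Change score minus covariate variance is 2(1 − r) − (1 − r²) = (1 − r)² for one quarter, and (V + 1 − 2r) − (V − r²) = (1 − r)² for the mean. This is never negative. The change score exceeds the unadjusted variance when 1 − 2r > 0, that is, when r < 0.5. With unequal SDs s_y (follow-up) and s_b (baseline), the gap is (s_b − r·s_y)², again never negative.

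**Size in SE terms.** The SE of the arm difference is √(2 × variance/138). For the five-quarter mean at r = 0.2 it is √(1.92/138) = 0.118 with the change score and √(0.64/138) = 0.068 with the covariate, in units of one quarter's SD.

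**Sensitivity to the correlation pattern.** If the correlation decays with lag as r × 0.9^(lag − 1), the five-quarter figures are 1.079 / 0.959 / 0.838 for the change score and 0.327 / 0.419 / 0.476 for the covariate: 70% / 56% / 43% less.

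**Adding the other two pre-camp quarters.** With the three-quarter mean as covariate, r² is replaced by 3r²/(1 + 2r). One quarter gives 0.91 / 0.73 / 0.51 and the five-quarter mean 0.27 / 0.25 / 0.19. At r from 0.1 to 0.3, the SE falls below that of the single-quarter covariate by only 1 to 4% (one quarter) or 3 to 12% (five-quarter mean). When r is weak, nearly all the gain comes from not subtracting.

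**Skewed costs.** Simulated gamma costs with 138 per arm and the three-quarter covariate gave SE ratios to the change score of 0.48, 0.52 and 0.58 for the five-quarter mean at r of about 0.11, 0.21 and 0.38, with no material bias. The formula gives √(0.255/1.08) = 0.49, √(0.274/0.96) = 0.53 and √(0.253/0.72) = 0.59 at r = 0.1, 0.2 and 0.4.

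**The case against.** The strongest reply is that the plan targets something else: the change within each arm relative to standard care. Subtracting baseline defines that quantity, and a baseline covariate does not tighten it. This stands. A reader might infer that the covariate helps whatever contrast is used. It does not: the gain belongs to the PLASMA-versus-control difference and requires a model containing both arms.

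Second, one baseline subtracted from all of a teen's follow-up costs is a constant within that teen. With complete data it cancels from any comparison between follow-up points. This also stands; only cost levels are affected.

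Third, the unlisted individual covariates could include baseline cost. In a joint model, regressing the change on baseline gives the same treatment effect as regressing follow-up cost on baseline. The plan, however, states neither the covariate nor the joint model.

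A reader might also infer that all three pre-camp quarters should form the main covariate, since they are collected anyway. The documents do not support that. Randomisation takes place upon enrolment (Section 4.1), so two of the three quarters follow it. Primary care providers in both arms are told of participation and then receive reports and alerts, so those quarters may include care prompted by the study and are not clearly standard care. Concealment of assignment (Section 3.2), and the absence of camp or contacts before month 6, make an arm difference in those quarters unlikely. That supports a sensitivity analysis.

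Finally, this concerns efficiency, not bias, in the last of five aims, and the plan makes no claim of power for cost.

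**Conclusion.** The point holds for the between-arm contrast in cost level, which is what the Aim 5 hypothesis concerns. Replacing the change score with a baseline covariate is worth 1.60/0.96 = 1.7, 1.20/0.84 = 1.4 and 0.80/0.64 = 1.25 times the sample size for one follow-up quarter at r = 0.2, 0.4 and 0.6. For the five-quarter mean it is worth 3.0, 2.0 and 1.5 times. These sizes rest on equal variances and a common r; the direction does not.

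Two stronger readings should be avoided. One is that quarterly costs here are known to be weakly correlated: the documents give no cost correlation, so the statement that subtraction is worse than no adjustment is conditional on r below 0.5. The other is that the plan will treat a non-significant difference as neutrality: no decision rule or margin for neutrality is given, so a wide interval is a risk to interpretation and not a stated rule.

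The change should be made, at moderate priority: it improves precision and aligns the main analysis with the hypothesis, but corrects no bias.

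**What to change.** In Section 10.1, Aim 5, make the following changes before outcome data are seen:

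- For each cost type, estimate the PLASMA-minus-control difference in one joint two-arm model. Use post-camp cost as the outcome, and treatment, follow-up time and pre-enrolment cost as covariates, allowing for repeated quarters within teen. Include pre-enrolment cost whether or not the arms look imbalanced on it.
- Define pre-enrolment cost as the cost in the three months before enrolment.
- Keep the within-arm change relative to standard care as a descriptive secondary result.
- Add a sensitivity analysis with the mean of the three pre-camp quarters as covariate. Note that two of them fall after randomisation and after provider notification has begun in both arms, though before camp or contacts.

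The data are already in the collection plan. The cost is SAP wording, a small amount of extra analysis, and a change of the main Aim 5 output from within-arm change to the between-arm difference.
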